1.4 Study Rationale

Unfortunately, 25% of CAH and 37% of EC patients go on to relapse after treatment with hormonal therapy. Relapse of CAH/EC patients after treatment with progesterone is thought to be related to progesterone resistance. Metformin is a generic oral anti-hyperglycemic. Recent evidence suggests that metformin reduces cancer risk and cancer deaths among diabetic patients (17-19). Based on preclinical *in vitro* and *in vivo* studies, metformin demonstrates anti-proliferative effects for both endometrial hyperplasia and cancer through inhibition of the mTOR pathway. Metformin has also demonstrated reversal of progesterone-resistance in endometrial cancer cell lines. In clinical data, metformin has been associated with decreased cellular proliferation (via Ki-67 staining) in endometrial cancer specimens of patients undergoing primary surgical management. Given our promising preclinical data, we hypothesize that the addition of metformin to standard LR-IUD progestin therapy will result in a CR rate at 6 months that is significantly higher than 50%. The comparator rate of 50% is based on results reported in the meta-analysis referenced earlier, and because a response rate significantly greater than this will be considered clinically meaningful by the investigators. The rate of CR at 6 months is our primary interest as this was the median time to response in the meta-analysis (12). Due to metformin's long term and wide spread use in patients with significant comorbidity, as well as proven safety and efficacy in healthy women with PCOS and non-diabetics, it is an ideal medication to evaluate in a population of non-surgical candidates.

In addition, our proposed clinical trial of metformin in combination with the LR-IUD will complement the proposed GOG trial in that we will (1) explore the potential activity of metformin in CAH and early stage EC patients as opposed to the advanced and recurrent patient population, and (2) we will investigate the combination of metformin with hormonal as opposed to cytotoxic therapy. If these study results are positive, we plan to propose a multicenter GOG trial of this treatment regimen, to establish a new standard of care for non-surgical patients with CAH/EC.

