being diagnosed with CAH/EC, non-surgical options that can maintain fertility and avoid operative risks are essential. Patients with major medical co-morbidity and poor performance status are not operative candidates, but require curative therapy for CAH/EC. A current accepted alternative treatment option for these patients is long-term progesterone therapy in the form of the levonorgestrel-releasing IUD (LR-IUD). Gunderson and colleagues conducted a meta-analysis of 45 studies (n=391 subjects) evaluating women with CAH or EC undergoing progestin therapy (systemic therapy or LR-IUD). For the group as a whole, the CR rate (as assessed via biopsy) was 66% for CAH and 48% for EC. (12) Median time to response was 6 months. Importantly, 25% of CAH and 37% of EC patients experienced relapse after initial response (12). In the literature for CAH/EC, an assessment of response is categorized by pathologic criteria on follow-up biopsies. A complete response (“disease regression”) is defined as no evidence of microscopic viable hyperplasia or cancer cells; stable disease (“disease persistence”) is defined as no change in biopsy status from prior to treatment; and progressive disease is defined as newly found or increase in grade of adenocarcinoma from the pre-treatment biopsy (12, 13).

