2.0 STUDY OBJECTIVES

2.1 Primary Objective

- 2.1.1** To compare the rate of CR at 6 months in non-surgical grade 1 EC and CAH patients receiving metformin + LR-IUD to 50%

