2.4 Endpoints

2.4.1 Primary Endpoint:

CR (“complete disease regression”), as defined by no evidence of microscopic viable hyperplasia or carcinoma on endometrial biopsy after 6 months of treatment.

2.4.2 Secondary Endpoints:

- CR, as defined above, at 6 months of treatment by CAH and EC
- CR, as defined above, at 12 months of treatment in group as a whole
- Adherence to at least 80% of scheduled doses over duration of prescribed treatment
- The type, severity and attribution of adverse events, by NCI Common Toxicity Criteria for Adverse Events (CTCAE), version (v) 4.0

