3.1.7 Understand study design, risks, and benefits and have signed informed consent

3.2 Exclusion Criteria

Any patient meeting any of the exclusion criteria at baseline will be excluded from study participation.

3.2.1 Evidence of renal dysfunction ($\text{Cr} > 1.5\text{mg/dL}$ or Cr clearance $< 60\text{mL/m}^2$) or liver dysfunction ($\text{AST/ALT} > 2\text{x upper limit of normal (ULN)}$)

3.2.2 Current use of progestin therapy (local, topical, or systemic) that has been ongoing for > 3 months

3.2.3 Myometrial invasion $>50\%$ or evidence of nodal or metastatic disease on baseline MRI (MRI only to be done for EC patients)

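### Is the 50% comparator for complete response at 6 months undermined because sections 1.4 and 8.2 never derive it from the meta-analysis?

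*Combined protocol and SAP*

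**What the plan says.** The primary objective in section 2.1 compares the 6-month CR rate in patients "receiving metformin + LR-IUD to 50"%. Section 2.4.1 assesses the endpoint "on endometrial biopsy after 6 months of treatment".

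Sections 1.4 and 8.2 give the same two grounds for 50%. One is the literature: "The comparator rate of 50% is based on results reported in the meta-analysis referenced earlier". The other is the investigators' judgment that a rate significantly above 50% would be clinically meaningful. Neither section shows a calculation.

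The source figures are in section 1.2. The meta-analysis is described as "evaluating women with CAH or EC undergoing progestin therapy (systemic therapy or LR-IUD"), so it pools routes of administration. It reports that "the CR rate (as assessed via biopsy) was 66% for CAH and 48% for EC", with no time point and no combined rate. Its only timing figure is "Median time to response was 6 months". Section 1.4 uses that figure to choose the assessment time: "The rate of CR at 6 months is our primary interest as this was the median time to response in the meta-analysis".

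Section 8.2 plans 30 evaluable patients, an exact test of 50% against 75% at two-sided 0.05, and 80% power. Section 8.3 adds exact 95% confidence intervals overall and by diagnosis.

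**The concern.** In a single-arm trial the benchmark carries the whole comparison, so its origin matters. A reader who tries to rebuild 50% from section 1.2 does not get there. The two quoted rates average 57% at the planned equal mix, they carry no assessment time, and they include systemic progestin as well as the IUD.

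If progestin alone gave 57% CR at 6 months, 50% would be too easy a target, and a result just over the line could arise with no contribution from metformin. A null of 57% would also need a larger trial: with 30 patients the cut-off would be 23 and power at 75% would be 51.4%, and 80% power would take 55 evaluable patients.

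The time scale adds to the doubt. Month 1 starts with metformin (section 6.1), which sections 4.2 and 6.3 allow up to 30 days after IUD placement. Section 3.2.2 excludes only "Current use of progestin therapy (local, topical, or systemic) that has been ongoing for > 3 months", so a patient may enter with up to 3 months of progestin already. Exposure to progestin at the month-6 biopsy can thus run from 6 months to about 3 + 1 + 6 = 10 months, and nothing says what exposure the 50% assumes.

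**Working it through.** **1. The plan's own figures.** Inputs from section 8.2: n = 30, null 0.50, alternative 0.75, exact test, two-sided 0.05. Let X be the number of complete responders.

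- At 0.50, P(X ≥ 20) = 0.0494 and P(X ≥ 21) = 0.0214. The smallest count with an upper tail of at most 0.025 is 21.
- At 0.75, P(X ≥ 21) = 0.8034, which agrees with the stated 80%.
- The widest exact 95% interval is at 15/30: 0.687 − 0.313 = 0.374, as stated.

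**2. The average of the quoted rates.** With 15 patients per diagnosis (section 1.1), (15 × 0.66 + 15 × 0.48)/30 = 17.1/30 = 0.57. To average 50%, the share w with hyperplasia would have to satisfy 0.66w + 0.48(1 − w) = 0.50, so w = 0.02/0.18 = 0.11, against a planned 0.50. Simple averaging at the trial's mix therefore does not produce the 50%.

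**3. From an untimed rate to month 6.** Assume the quoted rates are eventual rates, and let f be the fraction of responses that occur by month 6. The 6-month rate is then 0.57f. The documents do not say which patients the 6-month median covers.

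- Median over responders: f = 0.5, giving 0.57 × 0.5 = 28.5%.
- Median over all patients: half of all patients have responded by month 6, giving 50%, so f = 0.50/0.57 = 0.877.
- All responses by month 6: f = 1, giving 57%.

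**4. Chance of reaching 21 of 30 if metformin adds nothing.** X is the sum of a Binomial(15, 0.66f) and a Binomial(15, 0.48f).

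| f | 6-month rate | P(X ≥ 21) |
|---|---|---|
| 0.5 | 28.5% | 0.0000026 |
| 0.877 | 50% | 0.0201 |
| 0.892 | 50.8% | 0.025 |
| 1 | 57% | 0.0997 |

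The chance passes 2.5% only when more than about 89% of responses occur by month 6. For f = 1 to agree with a 6-month median among responders, at least half of all responses would have to fall exactly at month 6. Some clustering is possible if the source studies took biopsies at fixed visits, but nothing in the documents indicates that nearly all responses were complete by then.

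**5. What a positive result would show.** The exact 95% interval for 21/30 is 50.6% to 85.3%. It excludes 50% and includes 57%. The lower limit is 54.1% for 22/30 and 57.7% for 23/30, so 23 is the first count to clear 57%. The planned interval lets a reader see this directly.

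**6. The time scale.** Longer progestin exposure before the month-6 biopsy would tend to raise the background rate. Against that, section 3.1.1 requires histologically confirmed disease. A patient who has had progestin and still shows disease when the diagnosis is confirmed is selected for not having responded so far, which lowers her chance. The documents give neither the number of such patients nor a response curve, so neither the size nor the direction of the net effect can be worked out.

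**The case for a change.** The strongest case for a change is that the protocol does not rest on clinical judgment alone. It twice presents 50% as a figure from the progestin literature, its hypothesis concerns adding metformin to standard IUD treatment, and section 1.4 looks ahead to a larger trial aimed at a new standard of care. Readers may therefore take a rate above 50% to mean better than progestin alone. That reading depends on a step that is not shown, and the chance of a positive result without any metformin effect runs from 0.0003% to 10.0% across the readings above.

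Part of this stands. The derivation is missing, the quoted rates pool routes of administration, and the documents alone do not settle which patients the median covers. A positive result would not by itself establish that metformin adds to the IUD; a single-arm design could not do that with any benchmark.

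The rest does not carry a change. Sections 1.1, 1.4, 2.1, 8.1, 8.2 and 8.3 all word the hypothesis, objective or test against 50%, and none plans a claim of superiority over progestin alone. The 10.0% comes from the reading that fits the source's only timing figure least well. The natural remedy, one sentence of derivation or a relabelling of 50% as the investigators' own benchmark, would leave the test, the sample size and the data as they are.

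**Conclusion.** The observation is correct but minor: sections 1.4 and 8.2 cite the meta-analysis for 50% without showing how it follows. Nothing in the analysis depends on that step. The second ground, clinical meaning to the investigators, is enough for a fixed benchmark. The exact test has an upper-tail size of 2.1% at 50% and power of 80.3% at 75%, and a conclusion that CR at 6 months exceeds 50% is sound whatever the origin of the figure.

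The documents do not show 50% to be lenient. Under the two direct readings of the median it is either conservative (background 28.5%) or exact (50%). It becomes lenient enough to lift the chance of a positive result above 2.5% only beyond a background of about 50.8%, which needs more than about 89% of responses by month 6.

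This rests on three assumptions: the planned 15/15 mix, the quoted 66% and 48% being eventual rates, and those pooled rates being a fair guide to the IUD. The documents confirm only the first, as a plan. If the other two fail, the background rate could lie on either side of 50%, and the plan's stated claim would still be only that the rate exceeds 50%. The gap is one of explanation, which anyone reporting the trial can cover when describing the benchmark; changing the plan would gain nothing.

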1.5 Correlative Studies

We will explore the association of metabolic factors, expression of the metformin transporter proteins and key targets of the metformin/mTOR signaling pathway (i.e. Ki-67, AMPK, LKB1, AKT, PTEN, S6, 4E-BP1) with treatment response to metformin. Metabolic factors, including baseline body mass index (BMI), and glucose levels, will be documented and followed throughout treatment. Matched paraffin embedded tissues before and during metformin treatment will also be collected for immunohistochemical analysis of the metformin transporter proteins, Ki-67, and key components of the metformin/mTOR signaling pathway. Blood and urine will be collected at baseline and every 3 months during the study as a

means to (1) explore associations between metformin concentration levels and therapeutic outcomes, and (2) identify metabolic biomarkers of response to treatment through metabolomic profiling. Endometrial tissue will also be collected at the 6 month time point for analysis of metformin uptake into the endometrium.

2.0 STUDY OBJECTIVES

2.1 Primary Objective

- 2.1.1** To compare the rate of CR at 6 months in non-surgical grade 1 EC and CAH patients receiving metformin + LR-IUD to 50%

2.2 Secondary Objectives

- 2.2.1** To estimate the rate of CR at 6 months separately in grade 1 EC and CAH patients receiving metformin + LR-IUD
- 2.2.2** To estimate the rate of CR at 12 months in non-surgical grade 1 EC and CAH patients receiving metformin + LR-IUD
- 2.2.3** To document patient adherence to long-term (≥ 3 months) metformin administration
- 2.2.4** To describe safety of metformin + LR-IUD treatment

2.3 Exploratory Objectives

- 2.3.1** To explore changes in cellular proliferation as measured by the marker, Ki-67, from baseline to 6 months
- 2.3.2** To explore association between the level of expression of the metformin transporter proteins and key targets of the metformin/mTOR signaling pathway and CR status at 6 months
- 2.3.3** To perform a comprehensive unbiased profiling of metabolites by analyzing the metabolic “fingerprints” of the biofluids (i.e. serum and urine) and “footprints” of the tumor tissue pre- and post- 6 months of metformin treatment
- 2.3.4** To explore association between metabolic factors and metformin concentration levels in tumor tissue/blood/urine and CR at 6 months

2.4 Endpoints

2.4.1 Primary Endpoint:

CR (“complete disease regression”), as defined by no evidence of microscopic viable hyperplasia or carcinoma on endometrial biopsy after 6 months of treatment.

2.4.2 Secondary Endpoints:

- CR, as defined above, at 6 months of treatment by CAH and EC
- CR, as defined above, at 12 months of treatment in group as a whole
- Adherence to at least 80% of scheduled doses over duration of prescribed treatment
- The type, severity and attribution of adverse events, by NCI Common Toxicity Criteria for Adverse Events (CTCAE), version (v) 4.0

3.0 PATIENT ELIGIBILITY

3.1 Inclusion Criteria

Subjects must meet all of the inclusion criteria to participate in this study:

3.1.1 Histologically confirmed CAH or grade 1 EC

3.1.2 Females age \geq 18 years

3.1.3 ECOG Performance Status 0 – 4

3.1.4 Non-surgical candidates due to:

- Desire for fertility preserving treatment
- Unacceptable surgical risk as defined by:
 - American Society of Anesthesiologists Physical Status (ASA) \geq 4 and/or Perioperative Cardiac Risk $>$ 5%(45) and/or Perioperative Respiratory Failure Risk $>$ 5%(46)

AND

- Independent medicine or cardiology pre-op consultation concluding ‘high’ surgical risk.
- Patient determined to be a non-surgical candidate by the primary treating physician.

3.1.5 Planned treatment with the LR-IUD for CAH or grade 1 EC by primary physician

3.1.6 Women of childbearing potential (WOCBP) must have negative urine pregnancy test within 7 days of D1 of treatment

3.1.7 Understand study design, risks, and benefits and have signed informed consent

3.2 Exclusion Criteria

Any patient meeting any of the exclusion criteria at baseline will be excluded from study participation.

3.2.1 Evidence of renal dysfunction ($\text{Cr} > 1.5\text{mg/dL}$ or Cr clearance $< 60\text{mL/m}^2$) or liver dysfunction ($\text{AST/ALT} > 2\text{x upper limit of normal (ULN)}$)

3.2.2 Current use of progestin therapy (local, topical, or systemic) that has been ongoing for > 3 months

3.2.3 Myometrial invasion $>50\%$ or evidence of nodal or metastatic disease on baseline MRI (MRI only to be done for EC patients)

3.2.4 Mixed histology including clear cell, serous, undifferentiated or sarcomatous elements

3.2.5 Prior or current use of metformin within the past 3 months

3.2.6 History of hypersensitivity to metformin or history of discontinuation secondary to attributed adverse effects

3.2.7 Chronic (daily use for > 30 days) use of cimetidine (significant increase in metformin concentration and risk of lactic acidosis)

[figure not shown]
3.2.8 Iodinated contrast agents used in prior 48 hours (significant increase in metformin concentration and risk of lactic acidosis)

3.2.9 Pregnant or lactating

3.2.10 Recent (< 30 days) active, documented, cervical infection

4.0 TREATMENT PLAN

4.1 Schema

This is an open-label, single-arm, multi-center, study of the addition of metformin to the LR-IUD for treatment of non-surgical patients with CAH and grade 1 EC. While patients will be enrolled prior to dilation and curettage (D&C) and placement of the LR-IUD, both are standard of care, and will not be impacted by enrollment into the study.

Oral metformin therapy will be started within 1 week of LR-IUD placement and continued for 12 months unless disease progression occurs or the patient develops intolerance.

4.2 Dilation and Curettage (D&C)

As part of standard of care in treating CAH and EC with non-surgical progestin therapy, patients will undergo a D&C procedure for definitive diagnosis and therapeutic effect. During this procedure, the LR-IUD is placed. D&C is a safe, outpatient procedure that will be performed by a gynecologic oncology attending, fellow, or resident. In this procedure, the uterine lining tissue is removed with standard curette instruments. The main risk of this procedure is uterine perforation, which occurs at a rate of 1-2%. D&C would be performed regardless of study enrollment, and is not considered part of the current study. However, confirmation of CAH or EC will not be made, and therefore metformin will not be started, until after results of the D&C are read by the PI. This will occur within 3 days of receipt of the results and 7 days of the procedure and the patient will be informed that they can then initiate metformin. If a patient's provider does not feel

that they require a D&C procedure, the LR-IUD may be placed in clinic. The patient will undergo screening and pre-treatment testing at this time or the visit prior to the LR-IUD placement and will start the metformin within 30 days of IUD placement. Note that screening must occur within 30 days of starting treatment.

4.3 Treatment Dosage and Administration

All patients enrolled in this study will be non-surgical patients with planned LR-IUD treatment by the primary physician, per standard of care. Once the diagnosis of CAH or EC is confirmed by D&C, patients will be additionally treated with metformin as an investigational agent. Patients will be started on the standard clinical starting dose of metformin (850 mg once daily orally, titrated to twice daily over the course of one month (30 days)). This dose of 850mg twice daily will be continued for the duration of their prescribed study treatment. Patients will fill out a pill diary to record their usage. This diary will be provided to patients as a document separate from this protocol. Metformin will be obtained and dispensed by Investigational Drug Services at participating centers. The participating research sites have experience with metformin administration on clinical trials and will be well versed in managing dose escalation and side-effects. Patients will be instructed to take metformin with meals.

4.4 Toxicities and Dosing Delays/Dose Modifications

Any patient who receives treatment on this protocol will be evaluable for toxicity. Each patient will be assessed weekly for the first 2 weeks, then every 30 days thereafter for the development of any toxicity according to the Time and Events table (6.0). Toxicity will be assessed according to the NCI CTCAEv4. Dose adjustments should be made according to the system showing the greatest degree of toxicity.

We anticipate that metformin related hypoglycemia and GI disturbances will be the two most common side effects. Metformin will be discontinued if the patient experiences (1) a single grade 3 or higher metformin-related GI disturbance or grade 4 or higher hypoglycemic episode, or (2) two or more grade 2 side effects considered related to metformin therapy, or (3) if the patient requires a dose less than 850mg once daily. Patients may request to stop the drug at any time.

See section 8.2 for a stopping rule related to the proportion of patients who must discontinue metformin due to toxicities for the study to be suspended.

Metformin Toxicity Dose Reductions	
Event	Action
Hypoglycemia	
Grade 1-2	Patient education, avoidance of fasting states
Grade 3	Decrease to metformin 850mg once daily
Grade 4	Discontinue metformin, follow-up per protocol

GI Distress	
Grade 1-2	Patient education, avoidance of fasting states
Grade 3	Discontinue metformin, follow-up per protocol

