4.7 Duration of Metformin Therapy

The planned duration of metformin therapy is 12 months. Metformin treatment will be discontinued early in the following scenarios:

- Progression of disease, as defined by CAH progression to invasive adenocarcinoma or grade 1 EC progression to grade 2 or 3 EC, at any of the standard of care biopsies at 3, 6, and 9 months. In any of these cases, metformin will be discontinued within 3 days of results of the biopsy.
- Unacceptable toxicity as defined by a single grade 3 or higher GI disturbance attributed to metformin, a single grade 4 or higher hypoglycemia episode, 2 or more grade 2 toxicities attributed to metformin, or requirement for a dose below 850 mg once daily.

Response to therapy will be assessed at 3-month intervals. As per standard of care, endometrial biopsies will be performed every 3 months (+/- 2 weeks) to assess histology and grade to determine response. This will be the basis of whether therapy should continue. If the 3 month biopsy demonstrates disease progression, the patient will be removed from protocol directed treatment and followed-up per protocol, and treatment decisions will be at the discretion of the treating physician. Otherwise, therapy will continue through 6 months. If the 6-month or 9-month biopsy demonstrates complete response (complete disease regression) or partial response (partial disease regression), metformin will be continued until 12 months of total therapy is given. If the 6-month or 9-month biopsy demonstrates stable disease, continuation of metformin on study will be at the discretion of the treating physician. Please see the schema (section 4.1) for clarity.

In addition, treatment will be stopped in the setting of:

- Inter-current illness that prevents further administration of treatment
- Pregnancy
- Patient decides to withdraw from study treatment, **OR**
- General or specific changes in the patient's condition render the patient unacceptable for further treatment in the judgment of the investigator.

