8.2 Sample Size, Stopping Rule, and Accrual

The goal accrual is 32 patients (16 CAH, 16 EC) and we expect to enroll 1-2 patients/per month. Our power calculation and analysis will be based on 30 patients, assuming early discontinuation of 2 participants prior to 3 months of treatment. We estimate 18 months to complete accrual.

The primary objective of this study is to compare the CR rate at 6 months to a rate of 50% (the 50% is based on results reported in the meta-analysis referenced earlier, and because a response rate significantly greater than this will be considered clinically meaningful by the investigators). With a combined sample size of 30 evaluable patients with either CAH or grade 1 EC, and assuming a null CR rate of 50% and an alternative of 75%, we will have 80% power to conclude that the CR rate at 6 months is significantly higher than 50% using an exact test for a single proportion with a two-sided α of 0.05. Furthermore, the exact 95% confidence interval for the CR rate at 6 months will have a maximum width of 0.374. This means that the CR rate will be estimated within at least 18.7%. CAH and grade 1 EC represent a spectrum of neoplasia, which is why the two groups are being combined for the primary objective. The CR rate at 6 months will be estimated separately in the CAH and EC groups as a secondary objective.

Sequential boundaries will be used to suspend the trial if excessive toxicity is seen that requires discontinuation of metformin. If the study reaches a stopping boundary, it may be terminated by the PI, or submitted to the DSMC with a description of the toxicities and a rationale for why the study should be continued. At the patient level, metformin will be discontinued if a patient experiences: (1) a single grade 3 or higher metformin-related GI disturbance or grade 4 or higher hypoglycemic episode, or (2) two or more grade 2 side effects considered related to metformin therapy, or (3) if the patient requires a dose less than 850mg once daily. The accrual will be halted if the number of patients discontinuing metformin for one of the reasons above is equal to or exceeds b_n out of n patients who have been followed for toxicity for 3 months. This is a Pocock type stopping

boundary that assumes that a metformin discontinuation rate of 0.25 is acceptable, but anything $>25\%$ is unacceptable. If the true toxicity rate is equal to 0.25, the probability of crossing the boundary is 0.05.

Stopping Rule

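### The dose-change table in 4.4 has no effective action for grade 3 hypoglycemia at the starting dose and omits the two-or-more grade 2 stopping rule

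*Combined protocol and SAP*

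**What the plan says.** Section 4.3 gives the starting dose as "850 mg once daily orally, titrated to twice daily over the course of one month (30 days"; twice daily is then the dose for the rest of treatment.

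The text of 4.4 stops metformin under three criteria. The first is "a single grade 3 or higher metformin-related GI disturbance or grade 4 or higher hypoglycemic episode". The second and third are "two or more grade 2 side effects considered related to metformin therapy, or (3) if the patient requires a dose less than 850mg once daily". Section 4.7 states the same rule, including "2 or more grade 2 toxicities attributed to metformin, or requirement for a dose below 850 mg once daily".

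The table printed below the 4.4 text has these rows:

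- Hypoglycemia: grade 1-2, "Patient education, avoidance of fasting states"; grade 3, "Decrease to metformin 850mg once daily"; grade 4, stop.
- GI distress: grade 1-2, the same education entry; grade 3, stop.

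The table does not condition any row on the current dose, does not separate a first event from a repeat, and does not point back to the text.

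Section 8.2 repeats the three criteria and attaches the safety boundary to them: "The accrual will be halted if the number of patients discontinuing metformin for one of the reasons above is equal to or exceeds b_n", judged among the n patients followed for toxicity for three months. It gives a crossing probability of 0.05 when the true discontinuation rate is 0.25. Section 8.3 leaves out of the 6-month CR analysis any patient who did not complete three months of metformin, unless the cause was her disease.

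**The concern.** A dose-change table is what site staff are likely to use when an event occurs. Here it does not line up with the surrounding text in two situations. In one, the stated response to a grade 3 event has no effect. In the other, the table suggests that treatment goes on while the text ends it.

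This is first a matter of patient management, but it also has a statistical side. The boundary in 8.2 is driven by discontinuations that actually happen, so an event handled by education alone never enters the count. A toxicity stop before three months also removes the patient from the set used for the primary test. In a trial planned on 30 evaluable patients, a few patients handled differently could matter to both the safety monitoring and the response denominator.

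**Working it through.** **1. The boundary itself.** Inputs: b_n as printed in 8.2 (none for n = 1 to 3; 4 at n = 4, rising to 15 at n = 32) and p = 0.25. Let P_n(k) be the probability of k discontinuations among n patients without an earlier crossing. Then P_n(k) = (1 − p)·P_{n−1}(k) + p·P_{n−1}(k − 1), and any mass with k ≥ b_n is absorbed as a crossing. Summed to n = 32, the crossing probability is 0.0450, against the stated 0.05. A rebuilt Pocock-type boundary takes the smallest r whose binomial tail at 0.25 does not exceed a constant of about 0.0155. It matches all 32 printed entries. The next attainable boundary gives 0.0573, so 0.05 is a cap and 0.045 the attained level. The boundary is sound; the question is what reaches it as a count.

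**2. The grade 3 hypoglycemia row in milligrams.** Twice daily is 2 × 850 = 1,700 mg per day; once daily is 850 mg per day.

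- Patient on twice daily: 1,700 − 850 = 850 mg per day less.
- Patient on once daily: 850 − 850 = 0.

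The second case can arise at any time before the dose step, which is at most the first 30 of about 90 days in the three-month toxicity window (one third), and again after any earlier reduction.

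**3. Table and text side by side.**

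| Situation | 4.4 table | Text of 4.4, 4.7, 8.2 | Agreement |
|---|---|---|---|
| Grade 3 hypoglycemia on twice daily | Reduce to once daily | Not a stopping criterion (only grade 4 or higher is listed) | Yes |
| Grade 3 hypoglycemia on once daily | Instruction returns the same dose | First criterion not met; third criterion unsettled | Gap |
| First related grade 2 event | Education | No stop | Yes |
| Second related grade 2 hypoglycemia or GI event | Education | Stop | Not aligned |
| Grade 3 GI distress or grade 4 hypoglycemia | Stop | Stop | Yes |

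Two of the five situations are open. In the second row, the third criterion would apply only if a called-for decrease from 850 mg once daily is taken to mean that a lower dose is required. No section says whether it is.

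**4. From action to data.** In either open situation, a patient who is stopped counts toward b_n. If the stop falls before three months, she also leaves the 6-month CR set. A patient who continues does not count and, if she completes three months, stays in the set.

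**5. Can it be sized?** Let q1 be the share of patients meeting a stopping criterion on which table and text agree, q2 the share meeting one only through the grade 2 rule, and s the fraction of the latter whom sites actually stop. The counted rate is q1 + s·q2, with s between 0 and 1, so the grade 2 mismatch can only lower the count. For grade 3 events at once daily, the direction depends on how the third criterion is read. The documents give none of q1, q2 or s, and no rate of grade 3 hypoglycemia.

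**The case against.** The best defence is that the table and text do different jobs. The table gives one action per event and grade; the text adds a cumulative rule in mandatory terms, stands directly above the table and recurs in 4.7 and 8.2. Nothing says the table overrides it. A site would have to overlook three statements to keep treating after a second related grade 2 event. For grade 3 hypoglycemia at once daily, the third criterion is a plausible bridge, and 4.7 separately allows the investigator to stop treatment on judgment. Hypoglycemia is also described as rare (1.3.3, 4.4.1).

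Much of this stands, and it rules out several stronger readings.

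- A reader might infer that the grade 3 row contradicts the stopping text. It does not: on twice-daily dosing the two agree, and on once-daily dosing there is a gap that becomes a conflict only under one reading of the third criterion.
- A reader might infer that severity is inverted, since two grade 2 hypoglycemias end treatment and a single grade 3 does not. Table and text both keep the single grade 3 patient on treatment, so this is a clinical choice and not an inconsistency.
- A reader might infer that what b_n counts is undefined. Section 8.2 states its reasons explicitly.

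The defence does not remove the gap. The per-event reading is nowhere stated, and because the table prints a stop in two of its rows, it can be taken as complete. Investigator judgment and an unsettled reading of the third criterion do not amount to a stated action.

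**Conclusion.** The point holds as a misalignment of one table with the dosing and discontinuation text, in two specific situations: grade 3 hypoglycemia in a patient already at 850 mg once daily, and a second related grade 2 hypoglycemia or GI event. The first leaves the table's safety action without effect. The second leaves out a rule that three sections carry.

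The statistical consequence is conditional. If a site follows the table alone, toxicity is under-counted against the boundary and the 6-month CR set can change. The documents do not show that any site does so, and the size cannot be computed from them.

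Two figures might tempt a reader to size it. The 30% for GI effects in 1.3.3 has no grade split and includes bloating, flatulence and loss of appetite, so it does not bound the share with two or more grade 2 events. The boundary's steepness (crossing probability 0.012 at a counted rate of 0.20, 0.463 at 0.40) describes the boundary and says nothing about how far this misalignment moves the rate.

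It should be corrected because the rule as printed misfires and the correction is cheap. No view is taken here on which clinical action is right.

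**What to change.** Reconcile the 4.4 table with the text in 4.3, 4.4, 4.7 and 8.2 so that each of the two situations has exactly one action: grade 3 hypoglycemia in a patient already at 850 mg once daily (during titration or after a reduction), and a second related grade 2 event. The sponsor's clinical team should decide each action. If the decision alters any criterion in the 4.4 text, the copies in 4.7 and 8.2 need the same change.

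The cost is a short amendment to one table and the matching sentences. It needs no new data or procedures, and the arithmetic behind the printed boundary values is unaffected.
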